6.2 Exclusion Criteria

1. Concurrent anticancer therapy within 2 weeks of initiation of study treatment; except:
 - i. Endocrine therapy (SERM, aromatase inhibitor, fulvestrant, medical ovarian suppression therapy)
 - ii. Palliative radiotherapy for bone metastases < 1 week prior to study treatment
2. Unstable and symptomatic brain metastasis (Stable disease is defined as CNS radiographic study ≥ 4 weeks from completion of radiotherapy and ≥ 2 weeks from discontinuation of corticosteroids)
3. Non-hematologic adverse events from prior anticancer therapy that have not resolved to Grade ≤ 1 (CTCAE v 5.0), except for alopecia, vitiligo, pain, constipation if these symptoms existed during screening baseline.
 - i. Grade 3 or above neuropathy induced from prior treatment, that is not resolved to grade 2 or below despite best supportive care
4. Known clinically significant liver disease, including active viral, alcoholic, or other hepatitis; cirrhosis
5. Acute exacerbations of underlying condition within the last 12 months (requiring psoralen plus ultraviolet A radiation [PUVA], methotrexate, retinoids, biologic agents, oral calcineurin inhibitors; high potency or oral steroids)
6. Patients with known HIV infection. Testing for HIV is not required for study screening:
 - 1) CD4+ count <350 cells/uL; or 2) had AIDS-defining opportunistic infections < 12 months
7. Known active hepatitis B (chronic or acute) or hepatitis C infection. Testing for hepatitis is not required for study screening:

- i) Patients with past or resolved hepatitis B infection (defined as having a negative hepatitis B surface antigen [HbsAg] test and a NEGATIVE anti-HBc [antibody to hepatitis B core antigen] antibody test). Patient is eligible if anti-HBc is POSITIVE, but should sample for HBV DNA and referral to virologist to monitor for HBV reactivation
- ii) Patients with positive for hepatitis C virus (HCV) antibody and have positive polymerase chain reaction (PCR) for HCV RNA.
8. Severe infections within 4 weeks prior to study treatment, including but not limited to hospitalization for complications of infection, bacteremia, or severe pneumonia
9. Signs or symptoms of infection within 2 weeks prior to study treatment per treating physician and PI judgement.
10. Concurrent oral or IV antibiotics within 5 days prior to study treatment
 - * Patients receiving prophylactic antibiotics (e.g., for prevention of a urinary tract infection or chronic obstructive pulmonary disease) are allowed and eligible so long as the antibiotic is not prohibited with the study medication (See Tables 8).
11. Major surgical procedure within 28 days prior to study treatment or anticipation of need for a major surgical procedure during the course of the study.
12. Presence or history of interstitial lung disease or interstitial pneumonitis, including clinically significant radiation pneumonitis (i.e., affecting activities of daily living or requiring therapeutic intervention).
13. Long QT syndrome, family history of idiopathic sudden death or congenital long QT syndrome.
14. Clinically significant, uncontrolled heart diseases.
 - Unstable angina within 6 months prior to screening
 - Myocardial infarction within 6 months prior to screening
 - History of documented congestive heart failure (New York Heart Association functional classification III-IV)
 - Uncontrolled hypertension defined by a Systolic Blood Pressure (SBP) \geq 160 mm Hg and/or Diastolic Blood Pressure (DBP) \geq 100 mm Hg, with or without antihypertensive medication. Initiation or adjustment of antihypertensive medication(s) is allowed prior to screening
 - Ventricular arrhythmias
 - Supraventricular and nodal arrhythmias not controlled with medication
 - Other cardiac arrhythmia not controlled with medication
 - QTcF (QT interval corrected by Fridericia's formula) \geq 470 ms on the screening ECG (as mean of triplicate ECG)
15. Major surgery (e.g., intra-thoracic, intra-abdominal or intra-pelvic) within 4 weeks prior (2 weeks for resection of brain metastases) to starting study therapy or who have not recovered from side effects of such procedure.

[figure not shown]
16. Unable to swallow or absorb study drugs due to impairment of GI function or GI disease e.g., ulcerative diseases, uncontrolled nausea, vomiting, diarrhea, or malabsorption syndrome
17. Participants receiving treatment with any enzyme-inducing anticonvulsant that cannot be discontinued at least 1 week before first dose of capmatinib, and for the duration of the study.
18. Other severe, acute, or chronic medical or psychotic conditions, substance abuse or laboratory abnormalities that in the opinion of the investigator may increase the risk associated with study participation, or that may interfere with the interpretation of study results.
19. Pregnant or nursing (lactating) women
20. Women of child-bearing potential, defined as all women physiologically capable of becoming pregnant, unless they are using highly effective methods of contraception during dosing and for one month after stopping treatment. Highly effective contraception methods include:
 - Total abstinence (when this is in line with the preferred and usual lifestyle of the subject. Periodic abstinence (e.g., calendar, ovulation, symptothermal, post-ovulation methods) and withdrawal are not acceptable methods of contraception
 - Female sterilization (have had surgical bilateral oophorectomy with or without hysterectomy) total hysterectomy, or tubal ligation at least six weeks before taking study treatment. In case of oophorectomy alone, only when the reproductive status of the woman has been confirmed by follow up hormone level assessment
 - Male sterilization (at least 6 months prior to screening). For female subjects on the study, the vasectomized male partner should be the sole partner for that subject
 - Use of injected or implanted hormonal methods of contraception or placement of an intrauterine device (IUD) or intrauterine system (IUS), or other forms of hormonal contraception that have comparable efficacy (failure rate <1%), for example hormone vaginal ring or transdermal hormone contraception. Women are considered post-menopausal and not of childbearing potential if they have had 12 months of natural (spontaneous) amenorrhea with an appropriate clinical profile (e.g., age appropriate, history of vasomotor symptoms) or have had surgical bilateral oophorectomy (with or without hysterectomy) or tubal ligation at least six weeks before study entry. In the case of oophorectomy alone, only when the reproductive status of the woman has been confirmed by follow up hormone level assessment is she considered not of child-bearing potential.
21. Sexually active males will not be eligible unless they use a condom during intercourse while taking drug and for 3 months after stopping treatment and should not father a child in this period. A condom is required for all sexually active male to prevent them from fathering a child AND to prevent delivery of study treatment via seminal fluid to partner. In addition, male participants must not donate sperm for the time period specified above.
22. Participants receiving treatment with the following medications that cannot be discontinued at least 1 week prior to the start of treatment with study therapy and for the duration of the study:
 - a. strong inducers of CYP3A

- b. moderate inducer of CYP3A4
- c. strong CYP3A4 inhibitor
- d. concomitant use of a moderate CYP3A4 and P-gp dual inhibitor (verapamil).
- e. proton pump inhibitor. Neratinib may be taken at least 2 hours before or 10 hours after an H2-receptor antagonist, and 3 hours after antacids.
- f. P-gp substrates (such as digoxin, dabigatran, fexofenadine) or strong P-gp inducers (such as carbamazepine, phenytoin, rifampicin, and St. John's wort).
- g. Chronic immunosuppressive therapies including systemic corticosteroids. Steroids given for physiological replacement, as anti-emetics or inhaled as well as short course of oral/topical steroids given for allergic reactions or asthma flares are allowed.

23. No prior treatment with Capmatinib, Neratinib, or other HER2 directed tyrosine kinase inhibitor (for phase II patients only).

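### Three exclusion rules in section 6.2 are inconsistent as written: the bone-radiotherapy exception appears inverted, the neuropathy sub-item is redundant, and the brain-resection allowance has no effect

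*Combined protocol and SAP*

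**What the plan says.** All the text at issue is in section 6.2 (Exclusion Criteria) of the combined protocol and SAP.

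- **Item 1, prior therapy.** The stem reads "Concurrent anticancer therapy within 2 weeks of initiation of study treatment; except". The second listed exception, 1(ii), is "Palliative radiotherapy for bone metastases < 1 week prior to study treatment".
- **Item 3, residual toxicity.** The stem excludes "Non-hematologic adverse events from prior anticancer therapy that have not resolved to Grade ≤ 1 (CTCAE v 5.0), except for alopecia, vitiligo, pain, constipation", where the exceptions must have been present at screening baseline. Sub-item 3(i) then adds "Grade 3 or above neuropathy induced from prior treatment, that is not resolved to grade 2 or below despite best supportive care".
- **Items 11 and 15, surgery.** Item 11 excludes "Major surgical procedure within 28 days prior to study treatment", with no exception for the type of operation, and also excludes patients expected to need major surgery during the study. Item 15 excludes major surgery "within 4 weeks prior (2 weeks for resection of brain metastases) to starting study therapy", and also patients who have not recovered from the side effects of the operation.

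Inclusion 5 in section 6.1 asks for at least 2 weeks of washout after prior metastatic therapy. It says nothing specific about bone radiotherapy, residual neuropathy or surgery.

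**The concern.** An eligibility list should give one answer for each patient, and that answer should be the one the authors meant. Here the literal answer looks unintended for one topic. For the other two, a line that seems written to admit certain patients does not do so.

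At stake is who enters the trial. Staff who follow 1(ii) to the letter admit the more recent exposure and turn away the older one. Staff who take 3(i) or the parenthesis in item 15 as permission enroll patients whom the item 3 stem or item 11 excludes, and each such enrollment is open to challenge as a protocol deviation. Brain-metastasis patients can reach screening, because exclusion 2 bars only unstable and symptomatic disease, so the surgery conflict can arise in practice.

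**Working it through.** The plan gives no figure to reproduce. The check applies the windows and grade thresholds literally to test cases, counting the end day of each window as inside it.

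**1. Bone radiotherapy.** Inputs: a barred window of 2 weeks = 14 days (item 1 stem), and an exemption below 1 week = 7 days (item 1(ii)).

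| Days before dosing | Inside the 14-day bar? | Under 7 days, so exempt? | Result |
|---|---|---|---|
| 3 | yes | yes | allowed |
| 10 | yes | no | barred |
| more than 14 | no | not needed | allowed |

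Days 1 to 6 are allowed, days 7 to 14 are barred, and later days are allowed again. Eligibility is lost and then regained as the interval lengthens. The alternative reading, that radiotherapy in the last week is itself barred, conflicts with its place in a list of exceptions.

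**2. Neuropathy from prior treatment.** Inputs: the stem excludes anything above Grade 1 that is not on the list (alopecia, vitiligo, pain, constipation). Item 3(i) excludes Grade 3 or above that has not resolved to Grade 2 or below.

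| Persistent grade | Item 3 stem | Item 3(i) |
|---|---|---|
| 1 | not excluded | not excluded |
| 2 | excluded | not excluded |
| 3 or above | excluded | excluded |

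Everyone excluded by 3(i) is already excluded by the stem. The sub-item has a function only if Grade 2 neuropathy was meant to be acceptable, and the stem denies that.

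**3. Resection of brain metastases.** Inputs: 28 days (item 11); 4 weeks = 28 days in general but 2 weeks = 14 days for this operation (item 15).

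| Time since resection | Item 11 | Item 15 |
|---|---|---|
| up to 2 weeks (days 1 to 14) | excluded | excluded |
| 2 to 4 weeks (days 15 to 28) | excluded | not excluded, if recovered |
| over 4 weeks | not excluded | not excluded, if recovered |

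The two items disagree only in the middle row. There item 11 excludes every patient whom the parenthesis in item 15 would let through, so the shorter window never operates.

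**4. Does other text settle it?** Inclusion 5 does not, as noted. Exclusion 2 concerns the stability of brain metastases and sets no interval after surgery. The other eligibility text does not resolve any of the three points.

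**The case against.** The strongest reply is that exclusion criteria are cumulative: meeting any one excludes, and a narrower item grants no permission against a broader one. On that reading the text is determinate. Grade 2 neuropathy is out under the item 3 stem, a resection 2 to 4 weeks earlier is out under item 11, and 1(ii) yields a single answer at every interval. This stands. A reader might infer that these patients are both excluded and allowed, but the documents do not support that. The permission in 3(i) and item 15 is implied only, and 1(ii) is an odd exception to its stem, not a contradiction of it. What survives is that two clauses do no work and a third gives an implausible ordering.

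A reader might also infer that recent radiotherapy would distort the Phase Ib toxicity counts. Section 7.4 counts events at least possibly due to study therapy over 56 days, and under the 3+3 run-in one extra event moves 0/3 (escalate) to 1/3 (stay), or 1/3 to 2/3 (de-escalate). Those transitions are correct, but they hold for any misattributed event and do not measure this defect. The documents give no rate of qualifying events after palliative bone radiotherapy. Section 7.4 mostly requires Grade 3 or higher for non-hematologic events, section 12.1.2 allows attribution as unlikely or unrelated, and exclusion 18 lets the investigator exclude conditions that add risk or cloud interpretation. Section 8.2.2 does name earlier radiotherapy as a confounder of pneumonitis, but that was radiotherapy to the lung.

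Nor can it be said that the neuropathy conflict will be common. Inclusion 5 permits up to 6 prior metastatic lines, but no figure for residual neuropathy is given.

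Finally, the synopsis lists one site, which limits divergence between sites. It does not remove the risk of different decisions within that site.

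**Conclusion.** The point holds as an inconsistency in the eligibility wording that should be corrected. Following 1(ii) as written admits bone radiotherapy on days 1 to 6 before dosing and bars it on days 7 to 14. Item 3(i) excludes nobody beyond its stem. Item 15's allowance for brain-metastasis resection has no effect in the only window where it could matter, 2 to 4 weeks after the operation. The first is the most consequential, because obeying the text gives the seemingly unintended result. The other two do so only if staff read the narrower clause as permission.

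The effect is on who is enrolled and on consistency of eligibility decisions. Sample sizes, stopping boundaries and operating characteristics are unchanged, and no effect on toxicity counts can be quantified from the documents. The conclusion rests on a literal reading with end days counted as inside each window; another convention shifts the edges by a day and nothing else. It does not depend on which interval or grade is clinically right, and that is not judged here.

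**What to change.** The sponsor should reconcile the passages and choose the intervals and grades itself:

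- **Item 1(ii):** state unambiguously which intervals between palliative bone radiotherapy and study treatment are permitted.
- **Item 3:** give neuropathy one threshold, so that the stem and 3(i) agree.
- **Items 11 and 15:** give one surgery rule that says explicitly whether brain-metastasis resection is treated differently. Simply deleting either item would lose something. Item 15 alone carries the clause on patients who have not recovered from the operation, and item 11 alone carries the clause on anticipated surgery during the study. Both clauses should be kept.

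The cost is eligibility wording in the next amendment. The statistical design and analysis need no change.

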7.0 Study Procedures

7.1 Schema

***All patients with ER + breast cancer will start taking (or continue if they were already on) an aromatase inhibitor. Pre/peri-menopausal patients with ER + breast cancer will also receive ovarian suppression. The treating physician will choose the AI and ovarian suppression the patient will receive during the study duration.**

Figure 1. Study Schema

7.2 Dosing level and Drug Administration

All participants will receive two drugs (neratinib and capmatinib) during the study as scheduled per Schema. Capmatinib and neratinib will be provided by Novartis and Puma respectively, and not billed to the patient. Additionally, patients with ER+ breast cancer will receive endocrine therapy (AI +/- ovarian suppression). Endocrine therapy is standard of care (SOC), not provided by the study.

The Phase Ib portion of the trial will determine the Maximum Tolerated Dose (MTD) from the combination of dosing levels listed in Tables 2 and 3, starting at Dose Level (1,1) (capmatinib PO 400 mg twice per day and neratinib PO 120 mg on days 1-7, then 160 mg through end of treatment). The maximum accrual for phase Ib is 18 patients (including the possibility of adding up to 6 additional ER+/HER2 negative patients in a safety assessment of aromatase inhibitor treatment).

The Phase II portion of the trial will enroll 29 patients treated at the MTD determined from the phase Ib portion of the study.

Total accrual of this study will be up to 47 patients

Both drugs are oral agents and each study cycle will be 28 days.

Patient will take study drugs by mouth with or without food per cohort dosing. Neratinib will be taken once daily with food. Capmatinib will be taken twice daily about 12 hours apart (+/-2 hours) with or without food. Patients will have a medication diary to record daily study drug intake information for each cycle. The study manager will collect it at each clinic visit as source document.

Neratinib

Neratinib will be supplied as 40 mg tablets, equivalent to 48.31 mg neratinib maleate. Tablets are film-coated, red, oval shaped and debossed with 'W104' on one side and plain on the other side. 3 – 6 tablets daily will be prescribed based on patient's dose level. Tablets should be swallowed whole (tablets should not be chewed, crushed, or split prior to swallowing).

If a patient misses a dose, it should not be replaced, and the patient should be instructed to resume neratinib with the next scheduled daily dose.

Neratinib should be stored at controlled room temperature, 20°C to 25°C (68°F to 77°F); excursions permitted to 15°C to 30°C (59°F to 86°F).

Capmatinib

Capmatinib will be supplied at 200 mg and 150 mg tablets. Capmatinib should be taken twice daily with or without food. Tablets should be swallowed whole. Do not break, crush or chew the tablets.

If a patient misses or vomits a dose, instruct the patient not to make up the dose, but to take the next dose at its scheduled time.

Capmatinib should be stored at 20 – 25°C (68 – 77°F), excursions permitted between 15°C and 30°C (59 - 86°F). Protect from moisture.

Endocrine Therapy (for patients with ER+ breast cancer in Phase 1b and Phase II)

Patients with ER+ (defined at ER $\geq 10\%$) breast cancer will receive (start or continue) continuous aromatase inhibitor therapy by mouth dosed once daily. The aromatase inhibitor drug administered will be of physician's choice during the study duration. For pre-/peri-menopausal

women with ER+ breast cancer, ovarian suppression therapy of physician's choice will also be administered.

7.3 General Treatment Guidelines

If a toxicity is attributed to one of the study drugs, it may be held and the other drug(s) will still be given as scheduled. If a toxicity is not clearly linked to a single drug, then both neratinib and capmatinib may be held. The treating physician may withhold any of the drugs per their discretion and discussion with the principal investigator as needed to maintain patient safety while a toxicity is evaluated and treated. The drug should be resumed after appropriate toxicity management and dose reduced, if indicated as per Section 10 of the protocol.

Patients must receive at least 80% of the scheduled doses of each study medication to be considered evaluable for DLT. Patients with ER+ breast cancer must receive at least 80% of the scheduled dose of AI to be considered evaluable for DLT. However, any patient who experiences DLT, will be counted as a DLT regardless of how many doses received.

As study therapy is given continuously, missed days of treatment will not be made up. A cycle is defined as 28 days regardless of the number of days of treatment received.

In the event the patient experiences intolerable side effect(s) attributed to the endocrine therapy agent(s), the treating physician may withhold the agent per their discretion and discussion with the principal investigator as needed to maintain patient safety while a toxicity is evaluated and treated. The treating physician may change the AI agent administered and prescribe treatment for symptom control, as clinically indicated.

The following delays are allowed except during the DLT assessment period:

- 1) Up to 4 weeks due to study related AEs
- 2) Up to 8 weeks due to non-study related AEs

Unanticipated Dose Interruptions:

Interruptions due to non-study related issues (logistical, natural disaster, etc) are permitted in the case of logistical reasons not related to study therapy, up to 2 cycles of study.

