7.4 Dose Limiting Toxicity (DLT)

DLT is defined as any of the following possibly, probably, or definitely due to study therapy, assessed during the first 2 cycles [56 days]:

- Any death not clearly due to the underlying disease or extraneous causes
- Non- hematologic toxicity
 - Grade 3 or higher non-hematologic toxicity, Grade 3 diarrhea will be considered a DLT only if it lasts \geq 2 days despite prophylaxis and optimal standard medication and medical management.

- Grade 2 diarrhea lasting \geq 5 days despite prophylaxis and optimal standard medical management
- Pulmonary toxicity
 - Any grade of pneumonitis or ILD confirmed not attributable to infection or another etiology.
- Hy's Law case, defined as a patient meeting all of the following criteria:
 - ALT or AST \geq 3 x Upper Limit of Normal (ULN)
 - Total bilirubin >2 x ULN
 - Little or no evidence of cholestasis (alkaline phosphatase <2 x ULN)
 - No other identified explanation for the injury (such as hepatitis A, B, C, or other viral hepatic injury, alcohol ingestion, congestive heart failure).
- Neutropenic fever, defined as per CTCAE version 5.0:
ANC $<1000/\text{mm}^3$ and a single temperature of >38.3 degrees C (101 degrees F) or a sustained temperature of $>=38$ degrees C (100.4 degrees F) for more than one hour.
- Hematologic toxicity
 - Grade 4 neutropenia or thrombocytopenia >7 days
 - Grade 3 thrombocytopenia with bleeding
 - Grade 4 anemia

The targeted maximum DLT rate is 25%, and we will enroll patients in cohorts of size 3.

Table 4. Capmatinib and Neratinib overlapping toxicities

SOC	Capmatinib toxicity (Ref: CDS)	Neratinib toxicity (Ref: USPI and SmPC)
Congenital, familial and genetic disorders	Embryo-Fetal Toxicity	Embryo-Fetal Toxicity
Gastrointestinal disorders	Diarrhoea	Diarrhoea
	Vomiting	Vomiting
	Nausea	Nausea
	Constipation	Abdominal pain*
	Amylase increased	Stomatitis**
	Lipase increased	Dyspepsia
	Acute pancreatitis	Abdominal distension
		Dry mouth

General disorders and administration site conditions	Fatigue ¹	Fatigue
	Weight decreased	Weight decreased
	Back pain	
	Oedema peripheral ²	
	Non-cardiac chest pain ³	
	Pyrexia ⁴	
Hepatobiliary disorders	Alanine aminotransferase increased	Alanine aminotransferase increased
	Aspartate aminotransferase increased	Aspartate aminotransferase increased
	Blood bilirubin increased	Blood bilirubin increased

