Grade 1 (> ULN - 1.5 x ULN)	Maintain dose level
Grade 2 (> 1.5 - 3.0 x ULN)	Omit dose until resolved to ≤ grade 1 or baseline, then resume treatment at the same dose level.
Grade 3 (> 3.0 - 6.0 x ULN)	Omit dose until resolved to ≤ grade 1 or baseline, then resume treatment at ↓ 1 dose level.
Grade 4 (> 6.0 x ULN)	Permanently discontinue participant from capmatinib treatment
HEPATIC	
Isolated Total Bilirubin elevation*	
Grade 1 (> ULN - 1.5 x ULN)	Maintain dose level

Grade 2 ($> 1.5 - 3.0 \times \text{ULN}$)	Omit dose until resolved to \leq grade 1, then If resolved in ≤ 7 days, maintain dose level. If resolved in > 7 days, $\downarrow 1$ dose level
Grade 3 ($> 3.0 - 10.0 \times \text{ULN}$)	Omit dose until resolved to \leq grade 1, then If resolved in ≤ 7 days, $\downarrow 1$ dose level If resolved in > 7 days, permanently discontinue participant from capmatinib treatment
Grade 4 ($> 10.0 \times \text{ULN}$)	Mandatory: Permanently discontinue participant from capmatinib treatment
Isolated AST or ALT elevation	
Grade 1 ($> \text{ULN} - 3 \times \text{ULN}$)	Maintain dose level
Grade 2 ($> 3.0 - 5.0 \times \text{ULN}$)	Maintain dose level
Grade 3 ($> 5.0 - 20.0 \times \text{ULN}$)	Omit dose until resolved to \leq grade 1 (or \leq grade 2 if grade 2 elevation at baseline) then If resolved in ≤ 7 days, then resume treatment at the same dose level If resolved in > 7 days, resume treatment at $\downarrow 1$ dose level
Grade 4 ($> 20.0 \times \text{ULN}$)	Mandatory: Permanently discontinue participant from capmatinib treatment
Combined elevations of AST or ALT and Total Bilirubin ^{b,c,d}	
For participants with normal baseline ALT and AST and total bilirubin value: AST or ALT $> 3.0 \times \text{ULN}$ combined with total bilirubin $> 2.0 \times \text{ULN}$ without evidence of cholestasis or hemolysis OR For participants with elevated baseline AST or ALT or total bilirubin value: [AST or ALT $> 3 \times \text{baseline}$] OR [AST or ALT $> 8.0 \times \text{ULN}$], whichever is lower, combined with [total bilirubin $> 2 \times \text{baseline}$ AND $> 2.0 \times \text{ULN}$] without evidence of cholestasis or hemolysis	Mandatory: Permanently discontinue participant from capmatinib treatment
METABOLIC	
Amylase and/or lipase elevation	
Grade 1 ($> \text{ULN} - 1.5 \times \text{ULN}$)	Maintain dose level
Grade 2 ($> 1.5 - 2.0 \times \text{ULN}; > 2.0 - 5.0 \times \text{ULN}$ and asymptomatic)	Maintain dose level

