1. Patients in the first cohort are treated at dose level 1.
2. To assign a dose to the next cohort of patients, conduct dose escalation/de-escalation according to the rule displayed in Table 18. When using Table 18, please note the following:
 - a. “Eliminate” means eliminate the current and higher doses from the trial to prevent treating any future patients at these doses because they are overly toxic.
 - b. When we eliminate a dose, automatically de-escalate the dose to the next lower level. When the lowest dose is eliminated, stop the trial for safety. In this case, no dose should be selected as the MTD.
 - c. If none of the actions (i.e., escalation, de-escalation or elimination) is triggered, treat the new patients at the current dose.
 - d. If the current dose is the lowest dose and the rule indicates dose de-escalation, treat the new patients at the lowest dose unless the number of DLTs reaches the elimination boundary, at which point terminate the trial for safety.

[figure not shown]
e. If the current dose is the highest dose and the rule indicates dose escalation, treat the new patients at the highest dose.

3. Repeat step 2 until the maximum sample size of 18 is reached, or stop the trial if the number of evaluable patients treated at the current dose reaches 9.

Table 18. Dose Escalation/Deescalation Rule for the BOIN Design

Number of evaluable patients treated at current dose												
	1	2	3	4	5	6	7	8	9	10	11	12
Escalate if # of DLT <=	0	0	0	0	0	1	1	1	1	1	2	2
Deescalate if # of DLT >=	1	1	2*	2	2	2	3	3	3	3	4	4
Eliminate if # of DLT >=	NA	NA	3	3	3	4	4	4	5	5	6	6

Note. "# of DLT" is the number of patients with at least 1 DLT. When none of the actions (i.e., escalate, de-escalate or eliminate) is triggered, stay at the current dose for treating the next cohort of patients. "NA" means that a dose cannot be eliminated before treating 3 evaluable patients. "*" indicates the 3+3 design run-in.

$$* \text{ DLT rate} = \frac{\text{Total number of patients who experienced DLT at the current dose}}{\text{Total number of evaluable patients treated at the current dose}}$$

Figure 2. Flowchart for trial conduct using the BOIN design

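### Patients who lose more than 20% of doses to related toxicity short of a listed DLT leave the phase Ib dose-finding count, and the plan does not say how they enter the dose decision

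*Combined protocol and SAP*

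**What the plan says.** Protocol section 7.3 states: "Patients must receive at least 80% of the scheduled doses of each study medication to be considered evaluable for DLT". It adds that "Patients with ER+ breast cancer must receive at least 80% of the scheduled dose of AI to be considered evaluable for DLT". Neither sentence asks why doses were missed. One safeguard follows: "any patient who experiences DLT, will be counted as a DLT regardless of how many doses received". The same section lists permitted delays for adverse events but takes the DLT window out of that permission, without saying what follows if a delay occurs there.

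Section 7.4 defines DLTs as related events "assessed during the first 2 cycles [56 days"]. The list is broad. Its main item reads "Grade 3 or higher non-hematologic toxicity, Grade 3 diarrhea will be considered a DLT only if it lasts" two days or more despite treatment. It also includes Grade 2 diarrhea lasting at least "5 days despite prophylaxis and optimal standard medical management", pneumonitis of any grade, Hy's Law cases, neutropenic fever and certain hematologic events. It has no item for related toxicity that keeps a patient off drug.

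Section 10 provides for holds on events outside that list. For Grade 2 creatinine, Table 15 says: "Omit dose until resolved to ≤ grade 1 or baseline, then resume treatment at the same dose level". Table 15 also has holds for Grade 2 bilirubin, Grade 2 vomiting and Grade 3 neutropenia, and Table 12 interrupts neratinib for diarrhea of any grade with complicated features. Table 15 describes its entries as recommended unless marked mandatory.

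In section 13.1 the columns of Table 18 are headed "Number of evaluable patients treated at current dose", and the DLT-rate formula beneath it uses the same denominator. Section 13.2 has toxicity summaries submitted after every 3 evaluable patients.

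**The concern.** Read together, these sections exclude patients on the outcome being judged. Someone held off drug for a related event that is not a listed DLT is neither a DLT nor a patient who got through the window. That person leaves both numerator and denominator, and the wording about evaluable patients implies replacement, although the protocol does not say so outright.

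The phase Ib product is a maximum tolerated dose, which goes forward to 29 phase II patients. If such holds are common, the dose is chosen from patients who either had a listed DLT or managed at least 80% of their doses. Phase II would not reliably show the gap: the stopping rule in section 13.2 counts Grade 3+ toxicity, so Grade 2 events that interrupt dosing do not register there.

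**Working it through.** **1. What removes a patient.** The window is 56 days, with neratinib once daily (56 doses) and capmatinib twice daily (112 doses).
- Neratinib: 0.80 × 56 = 44.8, so 45 doses are needed. Missing 12 leaves 44/56 = 78.6%.
- Capmatinib: 0.80 × 112 = 89.6, so 90 doses are needed. Missing 23 leaves 89/112 = 79.5%.

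**2. The plan's own figures.** Inputs from section 13.1 and Appendix 1: target φ = 0.25, cohorts of 3, maximum 18, start at the third of five doses, uniform prior, elimination cutoff 0.95, 3+3 run-in, isotonic selection. The default BOIN alternatives are φ1 = 0.6φ = 0.15 and φ2 = 1.4φ = 0.35.
- Escalation boundary: ln(0.85/0.75) / ln[(0.25 × 0.85)/(0.15 × 0.75)] = 0.1968 (stated 0.197).
- De-escalation boundary: ln(0.75/0.65) / ln[(0.35 × 0.75)/(0.25 × 0.65)] = 0.2984 (stated 0.298).
- All 12 columns of Table 18 match.
- Table 19, selection of the true MTD in scenarios 1 to 4, with 10,000 simulated trials each: 49.3 / 52.6 / 59.7 / 55.6%, against stated 50.1 / 52.1 / 62.8 / 54.2%. Mean sample size: 17.15 / 16.99 / 16.63 / 17.05, against 17.2 / 17.1 / 16.6 / 17.1. Scenario 3 differs by 3.1 points, about two standard errors of a 1000-run simulation.
- This match needs the 9-patient stop to apply only when the decision is to stay at that dose. Stopping whenever 9 is reached gives mean sizes of 14.8 to 16.1.

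Table 19 is thus reproduced with no patient excluded for missed doses.

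**3. Effect of the exclusion.** Let p be the listed-DLT rate and q the chance that a patient without a listed DLT misses more than 20% of doses through related toxicity. The documents give no q; 0.1 to 0.3 is assumed.
- Dropped (current text): p / [1 − (1 − p)q]. At p = 0.25, q = 0.2: 0.25/0.85 = 0.294.
- Counted as events: p + (1 − p)q. Same values: 0.25 + 0.15 = 0.400.
- Kept as evaluable without DLT: p = 0.250.

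The selection figures use 6,000 simulated trials per setting. Dropped patients are replaced, and the cap of 18 applies to evaluable patients.

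| | q = 0.1 | q = 0.2 | q = 0.3 |
|---|---|---|---|
| Rate seen at p = 0.25, dropped | 0.270 | 0.294 | 0.323 |
| Rate seen at p = 0.25, counted as events | 0.325 | 0.400 | 0.475 |
| Scenario 4, % selecting level 2 or 3: dropped | 69.0 | 62.9 | 54.3 |
| Scenario 4: counted as events | 43.9 | 19.2 | 6.7 |
| Scenario 4: kept as non-DLT | 75.4 | 75.4 | 75.4 |
| Scenario 3, % selecting level 1 or higher: dropped | 73.8 | 66.8 | 58.1 |
| Scenario 3: counted as events | 53.0 | 29.2 | 13.1 |
| Scenario 3: kept as non-DLT | 78.8 | 78.8 | 78.8 |

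Letting q rise with dose (5/10/15/25/35% from level −2 to level 3) gives 62.4% dropped and 19.9% counted as events in scenario 4. A flat q suits capmatinib holds better, since Table 2 keeps capmatinib at 400 mg b.i.d. across levels 1 to 3.

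Replacement also has a cost in patients. In scenario 4 the mean number treated is 18.5 / 20.2 / 22.3 for q = 0.1 / 0.2 / 0.3, for about 17 evaluable.

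**The case against.** An 80% rule has a sound purpose: a patient with little exposure should not be credited with having tolerated the dose. Listed DLTs count whatever the exposure, and the list is wide enough that much toxicity causing a 12-day hold is already a DLT. Persistent Grade 2 diarrhea, for instance, qualifies at day 5. Most Table 15 holds are recommended rather than mandatory and concern capmatinib only, while Table 10 starts general neratinib holds at Grade 3. The affected patients stay in the safety data, all phase Ib adverse events are captured, and the IND medical monitor approves each change of dose level.

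All of this stands, and it narrows the point to related toxicity short of a listed DLT. It does not close the gap, because nothing says how the monitor should weigh these patients. Such holds are also plausible: section 8 reports creatinine increase in 27.1% of patients in a capmatinib study (all but one Grade 1/2) and vomiting in 26.2% on neratinib. Neither figure gives the Grade 2 share or the length of a hold.

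A reader might infer that the rule simply biases the MTD upward. The documents do not support that. The stated target is a 25% rate of listed DLTs. Dropping patients without a DLT shrinks only the denominator, which raises the observed rate and moves selection slightly down (scenario 4, q = 0.2: 62.9% against 75.4% if kept as non-DLT). Selection is too high only if the target is overall tolerability.

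**Conclusion.** The point holds in this form: the evaluability rule excludes patients for a reason tied to the outcome, and the plan does not say how related toxicity short of a listed DLT, when it costs more than 20% of doses, enters the dose decision. At p = 0.25 and q = 0.1 / 0.2 / 0.3, the current rule sees 0.270 / 0.294 / 0.323. That lies above the listed-DLT rate of 0.250 and below the overall intolerance rate of 0.325 / 0.400 / 0.475. The choice of handling can matter a great deal: in scenario 4 at q = 0.2, selection of level 2 or 3 ranges from 19.2% to 75.4%.

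These sizes rest on an assumed q, on replacement inferred from the evaluable wording, and on the reading of the 9-patient stop given in the working. At q = 0 there is no effect. It would also go too far to conclude that toxicity causing missed doses is never a DLT, or that section 10 compels all of these holds.

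**What to change.** Reconcile sections 7.3 and 7.4, section 10 and Table 18:
- Confine non-evaluable status and replacement to patients whose doses were missed for reasons unrelated to study therapy.
- Keep patients below 80% because of related toxicity in the dose decision, under a scoring rule that the sponsor fixes before any dose decision. Scoring them as DLTs is one option. The choice is a clinical one for the sponsor; section 8.2.2, for example, attributes transient creatinine rises on capmatinib to likely transporter inhibition.
- State what follows from a toxicity delay inside the DLT window.
- Report the number of such patients, by dose level and reason, in each cohort summary.
- Restate Table 19 under the chosen rule over a range of assumed hold rates.

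The cost is a protocol amendment and a rerun of the simulations, with no extra visits or procedures. If these patients are scored as DLTs, escalation can be slower and the selected dose lower, possibly by a material amount if such holds are common.
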